## 1. ADMINISTRATIVE INFORMATION

Protocol: Version 1 dated 1 June 2025

ClinicalTrials.gov register Identifier: NCT07245277

### 1.1 Document Version History

Version Date	Version	Author	Signature	Change Description	Reason/Comment
	1.0			Initial release.	Not applicable.

## 2. STUDY SYNOPSIS

This will be a randomized, multi-centered clinical trial. Participants will include preterm neonates diagnosed with neonatal sepsis who are treated with antibiotics. All eligible patients with parental consent, who cannot tolerate enteral feed will be assigned as Group 1 (antibiotic only). All eligible patients with parental consent, who can tolerate enteral feed enrolled into the trial will be randomized into two treatment groups. Group 2 will receive vitamin D as adjuvant therapy (400 IU) for seven days. Group 3 will receive vitamin D as adjuvant therapy (800 IU) for seven days. Each patient will undergo clinical assessments and blood examination at the beginning and end of each treatment period.

Study assessments will include the sepsis score (Tollner score and sepsis prediction score) and C-reactive protein examination.

### 2.1. Primary Objective

1. To determine the effect on the modified Tollner sepsis score among groups of preterm neonates with sepsis receiving adjuvant Vitamin D therapy at doses of 400 IU/day and 800 IU/day, compared to those receiving antibiotics alone.
2. To determine the effect on the Sepsis Prediction Score among groups of preterm neonates with sepsis receiving adjuvant Vitamin D therapy at doses of 400 IU/day and 800 IU/day, compared to those receiving antibiotics alone.

### 2.2. Secondary Objectives

To determine the effect on C-reactive protein (CRP) levels among groups of preterm neonates with sepsis receiving adjuvant Vitamin D therapy at doses of 400 IU/day and 800 IU/day, compared to those receiving antibiotics alone.

## 2.3. Study Population

### 2.3.1 Number of Participants

We aim to recruit minimum of fifty-seven neonates (19 neonates of each group) aged between 0 and 28 days old or maximum post menstrual age 42 weeks with sepsis.

### 2.3.2 Eligibility Criteria

Participants will be assigned to a randomised study treatment only if they meet all inclusion criteria and none of the exclusion criteria.

### 2.3.3 Inclusion criteria

The inclusion criteria for the case group in this study comprise neonates (aged 0–28 days or a maximum post-menstrual age of 42 weeks) with a gestational age of 28–36 weeks who are admitted to the neonatal high care unit (NHCU) and neonatal intensive care unit (NICU) of [name] General Hospital, Bandung, and Bandung Kiwari Regional Hospital, and meet the following criteria:

- Patients diagnosed with neonatal sepsis confirmed by blood or cerebrospinal fluid (CSF) culture, OR patients meeting the criteria for suspected sepsis based on a modified Tollner sepsis score of  $\geq 5$ , OR Sepsis Prediction Score  $\geq 3$ .
- Parents or legal guardians are willing to participate in the study and have signed the informed consent form.

### 2.3.4 Exclusion criteria

Participants meeting any of the following criteria will be excluded from the study:

- Patients with major congenital malformations, including anencephaly, encephalocele, holoprosencephaly, hydrocephalus, meningomyelocele, spina bifida, omphalocele, gastroschisis, or congenital heart disease.
- Patients who were initially able to tolerate enteral feeding but developed a medical condition requiring fasting (NPO/Nil Per Os) during the 7-day monitoring period.
- Patients who initially required fasting (due to a medical condition) but became able to tolerate enteral feeding during the 7-day monitoring period.

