## 2.4. Design and Intervention

This study is an analytical experimental study with a randomized controlled trial (RCT) design. All samples that meet the inclusion and exclusion criteria will be enrolled as study subjects. Subject characteristics data will be obtained from the patient's medical records. This was an open-label trial due to the nature of the nutritional intervention (NPO vs. enteral).

Subjects were subsequently allocated into three groups:

- Group 1: Subjects requiring medical fasting (NPO) due to their clinical condition, who received antibiotics alone.
- Group 2: Subjects able to tolerate enteral nutrition, who received antibiotics plus Vitamin D3 supplementation of 400 IU once daily for 7 days.
- Group 3: Subjects able to tolerate enteral nutrition, who received antibiotics plus Vitamin D3 supplementation of 800 IU once daily for 7 days.

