#### **3.4. Definition of analysis populations**

Data from this study will be analysed as a per-protocol analysis. Data from all participants who are randomised will be included in the per-protocol analysis.

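### Section 2.3.4 excludes infants for feeding changes after allocation, in opposite directions in the vitamin D and control groups, and section 3.4 does not settle whether they are analysed

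*Combined protocol and SAP*

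**What the plan says.** The exclusion list in 2.3.4 opens with "Participants meeting any of the following criteria will be excluded from the study". Two of its three criteria are events during follow-up:

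- The first applies to infants who are fed at entry: "Patients who were initially able to tolerate enteral feeding but developed a medical condition requiring fasting (NPO/Nil Per Os) during the 7-day monitoring period".
- The second applies to infants who are fasting at entry: "Patients who initially required fasting (due to a medical condition) but became able to tolerate enteral feeding during the 7-day monitoring period".

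Other sections treat the criteria as conditions for entry. Section 2.3.2 states: "Participants will be assigned to a randomised study treatment only if they meet all inclusion criteria and none of the exclusion criteria". Section 2.4 states "All samples that meet the inclusion and exclusion criteria will be enrolled as study subjects", and then "Subjects were subsequently allocated into three groups".

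Under the synopsis and 2.4, infants who cannot be fed enterally form Group 1 (antibiotics alone, not randomised). Infants who can be fed are randomised to 400 IU (Group 2) or 800 IU (Group 3). Both primary objectives in 2.1 compare the vitamin D doses with antibiotics alone, one on each sepsis score.

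On the analysis population, 3.4 has two sentences: "Data from this study will be analysed as a per-protocol analysis" and "Data from all participants who are randomised will be included in the per-protocol analysis". It does not define per-protocol.

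**The concern.** An exclusion that depends on what happens between Day 0 and Day 7 is selection after allocation. Because entry feeding status defines the groups, the two rules select on opposite courses. The vitamin D groups lose infants who go on to need fasting, and the control group loses infants who recover enough to feed. If feeding course is related to outcome, this alone opens a difference between vitamin D and control when the drug does nothing, and it does so in the contrast that both primary objectives name.

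The text also leaves the analysed population open. A reader cannot tell from 2.3.2, 2.3.4, 2.4 and 3.4 together which infants count, so the choice could be made after the data are seen, in an open-label trial.

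**Working it through.** **Step 1. Which infants each rule reaches.**

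| Rule in 2.3.4 | Groups it can reach | Conflict |
|---|---|---|
| Fed, then fasting | 2 and 3 only | Cannot be known before randomised assignment (2.3.2) or before enrolment and allocation (2.4); 3.4 keeps all randomised infants |
| Fasting, then fed | 1 only | Cannot be known before enrolment and allocation (2.4); 3.4 gives no explicit inclusion rule for non-randomised infants |

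**Step 2. Direction.** Entry on a modified Tollner score of at least 5, or a Sepsis Prediction Score of at least 3 (2.3.3), implies that a higher score is worse. Suppose a worse feeding course goes with a worse outcome. Removing the worst courses from vitamin D then lowers its mean, and removing the best courses from control raises the control mean. Both movements favour vitamin D. The plan does not say whether the outcome analysed is the Day-7 score or the change from Day 0; the condition must hold for whichever is used.

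**Step 3. Size, as illustration only.** The plan's figure of 19 per group (57 = 3 × 19) cannot be reproduced, because 2.6 gives no effect size or SD. It serves here only as the number recruited per group. Assumed, and not in the documents:

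- p, the share of a vitamin D group excluded (the worst courses);
- q, the share of Group 1 excluded (the best courses);
- r, the correlation of feeding course with outcome (positive = worse course, worse outcome);
- no drug effect, normal outcomes, a two-sided pooled t-test at 5%, and groups otherwise exchangeable, which this design does not provide.

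With φ the standard normal density and z its quantile, the spurious benefit in SD units is

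shift = r × [φ(z_p)/(1−p) + φ(z_q)/(1−q)].

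The bracketed terms are:

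- 10% excluded: 0.1755/0.90 = 0.195
- 20% excluded: 0.2800/0.80 = 0.350
- 30% excluded: 0.3477/0.70 = 0.497

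False-positive rates come from simulation with 40,000 replicates. Simulated shifts agreed with the formula to within about 0.003 SD.

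| Case | p | q | r | Shift (SD) | False positives |
|---|---|---|---|---|---|
| Both rules, no relation | 10% | 20% | 0 | 0 | 5% |
| Both rules | 10% | 10% | 0.3 | 0.3 × (0.195 + 0.195) = 0.12 | 6% |
| Both rules | 10% | 20% | 0.5 | 0.5 × (0.195 + 0.350) = 0.27 | 12% |
| Both rules | 10% | 30% | 0.5 | 0.5 × (0.195 + 0.497) = 0.35 | 16% |
| Group 1 loss only | 0 | 10% | 0.3 | 0.3 × 0.195 = 0.06 | 5% |
| Group 1 loss only | 0 | 20% | 0.5 | 0.5 × 0.350 = 0.18 | 8% |
| Group 1 loss only | 0 | 30% | 0.5 | 0.5 × 0.497 = 0.25 | 10% |
| Both rules, reversed | 10% | 20% | −0.5 | 0.27 against vitamin D | 12% |

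The Group 1 rows are the reading in which the second sentence of 3.4 is followed literally: randomised infants stay, and only recovering controls are lost.

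**Step 4. Relation to the existing gap.** Group 1 is formed by clinical condition, so it may differ from the fed groups at the outset. The selection shift adds to that gap. If Group 1 were 0.5 SD worse to begin with, rejection would be 32% with no exclusions and 65% with 10%/30% and r = 0.5; the first 32% belongs to confounding, not to these rules. If Group 1 were 0.25 SD better, the same exclusions would turn that into an apparent vitamin D benefit of 0.346 − 0.25 = 0.10 SD.

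**The case against.** The best defence is that 3.4 keeps every randomised infant. Read literally, it does, and the fed-then-fasting part of the bias disappears. But that reading contradicts 2.3.4 and sits beside an undefined per-protocol label, and it does not protect Group 1, which is not randomised. A reader might go further and infer that 3.4 leaves Group 1 out altogether. That is too strong: its first sentence covers the data of the whole study. What is missing is a definition and an explicit inclusion rule.

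A second defence is that the comparison with Group 1 is confounded by design, so a further shift hardly matters. The confounding is real, and no change to 2.3.4 removes it. The selection is still a separate defect: it can enlarge, mask or reverse the existing gap, and adjustment for Day-0 covariates does not bring back infants excluded later.

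Third, size is unproven. This stands. All rates and correlations above are assumed, and the mildest case moves the error rate only from 5% to 6%, or leaves it at about 5% if only Group 1 infants are lost.

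A reader might also infer that the 400 IU versus 800 IU comparison is safe because one rule applies to both arms, or that it is biased too. The documents support neither. The rule conditions on an event after randomisation that dose could affect. Section 3.5 lists gastrointestinal adverse events, but nothing says whether these lead to fasting or differ by dose.

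**Conclusion.** The point holds in conditional form. Section 2.3.4 states exclusions that depend on events after allocation, and 2.3.2, 2.4 and 3.4 cannot all be followed alongside it. If both rules are applied, vitamin D versus antibiotics alone is biased towards vitamin D whenever a worse feeding course goes with a worse value of the analysed outcome. It is tempting to conclude that the trial will favour vitamin D. The documents do not go that far: they give no exclusion rates, do not show the relation between feeding course and outcome, and do not say which sentence of 3.4 prevails.

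Confidence is high for the contradiction and for the conditional direction, and low for size. The illustrated shifts rest wholly on the stated assumptions, including exchangeable groups. For 400 IU versus 800 IU, bias is neither shown nor ruled out.

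**What to change.** 1. Limit 2.3.4 to facts known at Day 0, and reconcile 2.3.2, 2.3.4, 2.4 and 3.4.
2. In 3.4, define the primary analysis set as all randomised infants by allocated dose, plus Group 1 by Day-0 feeding status.
3. Collect both sepsis scores and CRP at Day 7 whatever happens to feeding, and report feeding changes by group.
4. Keep the subset with no feeding change as a labelled sensitivity analysis.
5. State that comparisons with Group 1 remain non-randomised and confounded. This change removes only the selection after allocation; it does not restore a 5% error rate.
6. Reconcile item 6 of the study protocol list in 2.7, which ties vitamin D to tolerating enteral feeds, with keeping Group 1 infants who begin feeding. How those infants should be treated is not a matter for this review.

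The cost is mainly wording. Section 2.7 already schedules Day-7 blood, and the synopsis schedules assessment at the end of the treatment period, although that timing is unclear for an infant whose treatment is interrupted and should be fixed at Day 7. The downside is that the estimate will include infants with interrupted treatment and possibly Group 1 crossover, so it may be diluted by an unknown amount. Sections 2.4, 2.5.1 and 3.7 use the past tense, so Day-7 data may be missing for any infants already excluded; their number should be reported by group.

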## 2.4. Design and Intervention

This study is an analytical experimental study with a randomized controlled trial (RCT) design. All samples that meet the inclusion and exclusion criteria will be enrolled as study subjects. Subject characteristics data will be obtained from the patient's medical records. This was an open-label trial due to the nature of the nutritional intervention (NPO vs. enteral).

Subjects were subsequently allocated into three groups:

- Group 1: Subjects requiring medical fasting (NPO) due to their clinical condition, who received antibiotics alone.
- Group 2: Subjects able to tolerate enteral nutrition, who received antibiotics plus Vitamin D3 supplementation of 400 IU once daily for 7 days.
- Group 3: Subjects able to tolerate enteral nutrition, who received antibiotics plus Vitamin D3 supplementation of 800 IU once daily for 7 days.

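### The open-label reason does not cover the randomised 400 versus 800 IU comparison, and no masking is described for whoever completes the two primary scores

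*Combined protocol and SAP*

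**What the plan says.** Section 2.4 declares the trial open-label for a single reason: "This was an open-label trial due to the nature of the nutritional intervention (NPO vs. enteral"). The same section then defines three groups. The fasting one is described as follows: "Group 1: Subjects requiring medical fasting (NPO) due to their clinical condition, who received antibiotics alone". The other two are both fed and both given vitamin D3 alongside their antibiotics. For the higher amount the text reads: "Subjects able to tolerate enteral nutrition, who received antibiotics plus Vitamin D3 supplementation of 800 IU once daily for 7 days". The entry for Group 2 is worded in the same way except that the amount is 400 IU.

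The synopsis (section 2) shows which of these are randomised. Infants "who cannot tolerate enteral feed will be assigned as Group 1 (antibiotic only"), whereas infants "who can tolerate enteral feed enrolled into the trial will be randomized into two treatment groups".

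Section 2.1 names two primary outcomes, the modified Tollner score and the Sepsis Prediction Score, each comparing the two doses with antibiotics alone. On assessment, the synopsis says: "Each patient will undergo clinical assessments and blood examination at the beginning and end of each treatment period".

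Section 2.5 has blinding in its title but contains only subsection 2.5.1, on randomisation. It says that the sequence is computer-generated and that the author allocates. No section names the scorer or describes masking of scorer, carer, parent or analyst.

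**The concern.** A reason for leaving a trial open has to apply to the comparison left open. Fasting cannot be concealed, so the stated reason is understandable for Group 1 against the fed groups. Between Groups 2 and 3 feeding does not differ; the only stated difference is the daily amount of vitamin D3. The plan gives no reason for leaving that contrast open and no safeguard for the scoring.

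The 400 versus 800 IU contrast is the only one protected by randomisation. If the person scoring Day 7 knows the dose, a systematic leaning can appear as a dose effect. If the same person completes both scores, the leaning can move both primary outcomes together, and section 3.6 plans no multiplicity adjustment.

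**Working it through.** **Step 1. Does the stated reason reach the randomised arms?** From section 2.4 and the synopsis:

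| Feature | Group 1 | Group 2 | Group 3 |
|---|---|---|---|
| Feeding | fasting | enteral | enteral |
| Vitamin D3, once daily for 7 days | none | 400 IU | 800 IU |
| How assigned | by feeding intolerance | randomised | randomised |

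The feeding row differs only between Group 1 and the other two. The reason therefore does not reach Group 2 versus Group 3.

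**Step 2. Does another section fill the gap?** Section 2.5 covers allocation only. Section 2.7 describes blood sampling and laboratory handling but not who scores. Section 3 contains nothing on masking. No redaction or missing-figure marker stands in 2.4 or 2.5.

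**Step 3. Which scores precede allocation?** Section 2.3.2 requires eligibility before assignment, and section 2.3.3 admits infants by culture, by a modified Tollner score of at least 5 or by a Sepsis Prediction Score of at least 3. For an infant entering on a score, that score exists before any dose is allocated. An infant entering on culture alone has no such guarantee unless the plan requires the Day-0 scores first. The exposure is therefore mainly at Day 7.

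**Step 4. The plan's own figure.** Section 2.6 gives 19 per group (3 × 19 = 57) at 95% confidence and 80% power, with no effect size or SD, so 19 cannot be reproduced. Solved backwards with the two-sided normal approximation, d = √(2/19) × (1.960 + 0.842) = 0.909 SD. Any d from 0.909 to 0.933 SD rounds up to 19. With the t distribution, 80% power at 19 per arm corresponds to 0.934 SD. The masking point does not depend on this figure; it serves only as a yardstick below.

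**Step 5. Illustration of what a scoring shift would do.** Inputs: n = 19 per arm (section 2.6) and 5% significance (section 2.6). Assumed, because the plan does not state them: a two-sided two-sample t-test, no true dose effect, and a systematic shift of b SD between arms.

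Noncentrality = b × √(n/2) = b × √9.5 = b × 3.082, with 2 × 19 − 2 = 36 degrees of freedom. The rejection probability is the two-tail probability of the noncentral t beyond the 5% critical value.

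| Assumed shift b (SD) | Noncentrality | Chance of p < 0.05 |
|---|---|---|
| 0 | 0 | 5.0% |
| 0.1 | 0.308 | 6.0% |
| 0.2 | 0.616 | 9.2% |
| 0.3 | 0.925 | 14.7% |
| 0.5 | 1.541 | 32.3% |

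The largest shift is 0.5/0.934 = 54% of the difference that the trial can detect with 80% power, so it is the severe end of the range and not a small leaning.

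**The case against.** A reader might infer that the dose arms are scored unmasked by the person who allocated them. The documents do not say so. They do not name the scorer, and open-label status does not by itself settle whether the assessor is masked. The supportable statement is that masking of the scorer is not described in a trial declared open without exception.

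A reader might also take both scores to be matters of bedside judgement. No section lists their components. The synopsis pairs clinical assessment with blood examination, and section 2.7 collects haematology, smear morphology and CRP on both days. Any laboratory components would be less open to a scorer's leaning, so the exposed part of each score is unknown.

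The bias sizes have no anchor in the plan, and the plan gives no reason why a scorer would favour one active dose over the other. Nor can bias be called avoidable on the documents alone, since formulation and volume are not described and product masking cannot be confirmed as feasible.

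The remedy has a trap of its own. Masking only Groups 2 and 3 would make the scoring method differ from Group 1 in the contrasts that section 2.1 names as primary. Dose masking of Day-0 scores completed before allocation would serve no purpose. Chart-based scoring also cannot remove a leaning already recorded by staff who know the dose.

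All of these stand. They limit the claim about size and shape the remedy. They do not supply a reason for leaving the randomised contrast open or fill the gap in section 2.5.

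**Conclusion.** The point holds in this form: the stated open-label reason does not apply to the randomised comparison, the author allocates, and masking of whoever completes the primary scores is not described. Detection bias is possible in whatever part of the scores depends on clinical judgement.

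Its size cannot be determined from the documents. The rates of about 9%, 15% and 32% are conditional on assumed shifts of 0.2, 0.3 and 0.5 SD, 19 per arm, no true effect and a two-sided t-test. They are not estimates of this trial's error rate. The change is worth making because it is cheap and protects the only randomised contrast. It leaves the non-randomised comparison with Group 1 as weak as before.

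**What to change.** In section 2.4, limit the open-label reason to Group 1 versus Groups 2 and 3.

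In section 2.5, add wording to this effect:

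> The Day-7 modified Tollner and Sepsis Prediction Scores are completed in all three groups by one and the same procedure. The scorer is an investigator already on the study team who neither allocates nor holds the randomisation list. Scoring uses the charted findings and laboratory values with the vitamin D order and the 25(OH)D results removed. The score sheet records whether the scorer knew the dose. Day-0 scores are completed and locked before allocation.

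Removing the 25(OH)D results matters because section 2.7 measures them on Day 0 and Day 7 and they could reveal the dose. Locking the Day-0 scores before allocation makes dose masking at baseline unnecessary, including for infants who enter on culture alone.

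Cost: protocol wording, a score sheet without the dose, and some coordination within the team or between the two hospitals. No matched product and no additional assessor are needed. Three limits remain and should be stated: findings charted by staff who know the dose may already carry bias, fasting status in Group 1 is not masked, and the comparison with Group 1 stays non-randomised.

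### Group 1 is filled by feeding intolerance, not by randomisation, so every comparison with antibiotics alone is confounded with feeding status; only 800 versus 400 IU is randomised

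*Combined protocol and SAP*

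**What the plan says.** The Synopsis (section 2) sends infants "who cannot tolerate enteral feed will be assigned as Group 1 (antibiotic only", while those "who can tolerate enteral feed enrolled into the trial will be randomized into two treatment groups". Section 2.4 repeats the rule, "Group 1: Subjects requiring medical fasting (NPO) due to their clinical condition, who received antibiotics alone", and labels the whole study: "This study is an analytical experimental study with a randomized controlled trial (RCT) design". It explains the lack of blinding in these words: "This was an open-label trial due to the nature of the nutritional intervention (NPO vs. enteral". Section 2.5.1 mentions a computer-generated sequence without saying which groups it covers.

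The primary objectives (section 2.1) concern the modified Tollner score and the Sepsis Prediction Score in infants "receiving adjuvant Vitamin D therapy at doses of 400 IU/day and 800 IU/day, compared to those receiving antibiotics alone". Section 2.2 uses the same comparator: "To determine the effect on C-reactive protein (CRP) levels among groups of preterm neonates with sepsis". The 800 versus 400 IU comparison is not named separately.

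On who is analysed, section 2.3.2 states: "Participants will be assigned to a randomised study treatment only if they meet all inclusion criteria and none of the exclusion criteria". Section 2.3.4 then excludes fed infants who come to need fasting, and fasting infants who become able to feed, during the 7 days of monitoring. Section 3.4 calls the analysis per-protocol and includes everyone who was randomised.

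**The concern.** An RCT label and objectives worded as effects tell the reader that the groups differ only by chance and by treatment. Here the comparator group differs by rule: its infants could not be fed. A difference in sepsis score or CRP could come from feeding status, from whatever made fasting necessary, or from vitamin D. That fasting infants are sicker is an inference from the wording about their clinical condition; the reasons for fasting are not listed. There is no fed group on antibiotics alone and no planned adjustment. The baseline table in section 4.2 does not list Day-0 scores or CRP, so a reader could not see an imbalance in the outcomes themselves.

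The exclusions in section 2.3.4 add a second problem. Applied after entry, they remove infants from Group 1 who become able to feed and infants from the vitamin D groups who come to need fasting. That selects on clinical course, plausibly in favour of vitamin D. In the vitamin D groups it is also exclusion after randomisation, which weakens the dose comparison.

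**Working it through.** **1. The plan's own figure.** Section 2.6 gives 19 per group (57 in total) at 95% confidence and 80% power, with no effect size, SD or sidedness, so 19 cannot be reproduced. Solved backwards (two-sided), d = (1.960 + 0.842) × √(2/19) = 0.91 SD by the normal formula, and 0.93 SD with the t distribution on 36 degrees of freedom. A one-sided test would give about 0.81 SD (normal formula). The concern does not depend on this figure.

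**2. What is randomised.**

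| Contrast | Named in objectives | Randomised |
|---|---|---|
| 400 IU v antibiotics alone | yes | no |
| 800 IU v antibiotics alone | yes | no |
| 800 v 400 IU | not separately | yes |

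At the planned minimum, 19 + 19 = 38 of 57 infants (67%) are randomised.

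**3. Can adjustment separate feeding from vitamin D?** Let F = 1 for fasting at entry, and let A and B indicate 400 and 800 IU. By the assignment rule F = 1 − A − B for every infant. The design matrix (intercept, A, B, F) therefore has rank 3 for 4 columns. No regression can estimate a vitamin D effect separately from feeding.

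**4. Illustrative false-positive rate.** Assume no drug effect, a prognosis gap of δ SD in the Day-7 value, 19 v 19 analysed and an unadjusted two-sided 5% t-test. The noncentrality is δ√(19/2) = 3.08δ, with 36 degrees of freedom.

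| Assumed δ (SD) | 0.25 | 0.5 | 0.75 | 1.0 |
|---|---|---|---|---|
| Rejection rate | 12% | 32% | 61% | 85% |

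**5. Illustrative effect of the section 2.3.4 exclusions alone.** Assume groups equal at entry. The best-doing fraction p of Group 1 and the worst-doing fraction p of a vitamin D group are excluded, and clinical course correlates ρ with the Day-7 score. With z the p-quantile of the standard normal and λ = φ(z)/(1 − p), the raw gap is 2ρλ and the SD after selection is √(1 − ρ² + ρ²(1 + zλ − λ²)). For ρ = 0.5:

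| p | λ | Raw gap | Gap in SD after selection | Rejection rate |
|---|---|---|---|---|
| 5% | 0.109 | 0.109 | 0.11 | 6% |
| 10% | 0.195 | 0.195 | 0.20 | 9% |
| 20% | 0.350 | 0.350 | 0.37 | 20% |

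Simulation of the truncated data gives 6.3%, 9.2% and 19.5%. For ρ from 0.3 to 0.7 the gap is 0.12 to 0.29 SD (rejection 6% to 14%) at p = 10%, and 0.21 to 0.55 SD (10% to 38%) at p = 20%.

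If section 3.4 prevails and all randomised infants are kept, only Group 1 is selected. At ρ = 0.5 and p = 20% the raw gap is then ρλ = 0.5 × 0.350 = 0.175 and rejection about 8%.

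**6. Direction.** The SAP names no test and does not say whether the endpoint is the Day-7 value or the change from Day 0. Assume Group 1 is worse by g = 0.5 SD at Day 0 and h = 0.25 SD at Day 7, with unit SDs, correlation r and no drug effect. Positive values favour vitamin D.

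| Analysis | Formula | r = 0.3 | r = 0.5 | r = 0.7 |
|---|---|---|---|---|
| Day-7 value | h | +0.25 | +0.25 | +0.25 |
| Change | (h − g)/√(2(1 − r)) | −0.21 | −0.25 | −0.32 |
| Adjusted for Day 0 | (h − rg)/√(1 − r²) | +0.10 | 0 | −0.14 |

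The same data can favour either side, and the Day-0-adjusted result can also fall on either side of zero.

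**7. Analysis set.** Section 2.3.2 permits assignment only when no exclusion applies, but two exclusions in section 2.3.4 can be known only after entry. Section 3.4 keeps all randomised infants. These cannot all be followed. Read literally, section 3.4 also omits Group 1, which is never randomised. That is probably loose wording, since section 3.1 covers all objectives and the section 4.2 table has a control column, but it leaves Group 1's analysis set undefined.

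**The case against.** The assignment rule is stated openly, and fasting infants cannot readily receive an enteral supplement. Both points are true. They explain why Group 1 goes untreated, but do not make it a fair control or justify the RCT label for that contrast. The section 2.4 remark on fasting versus enteral feeding is offered as the reason for open-label conduct, so it should not be read as an admission of confounding.

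The illustrations rest on assumed values. Selection of 5% from each side barely moves the error rate, keeping all randomised infants shrinks the effect further, and the sign reversal uses one chosen pair of gaps. These limits stand: the calculations show what could happen, not what will.

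Adjustment for Day-0 values does not cure the problem either, as step 6 shows. This also stands, and is why the adjusted contrast should carry no causal claim. The objectives as worded would need an antibiotics-only group with the same feeding status as the vitamin D groups. Whether that is feasible is for the sponsor.

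The analysis-set conflict is a separate fault that would exist even with a randomised control. It is included because it acts on the same comparisons. None of this removes the central point.

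**Conclusion.** The concern holds. Every comparison named in the objectives uses a non-randomised group that differs completely from the vitamin D groups in feeding status at entry. The RCT label is justified only for 800 versus 400 IU. This follows from the plan's own text and needs no assumption.

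The size and direction of the bias cannot be derived from the documents. Under the stated assumptions, a moderate gap of 0.5 SD raises the false-positive rate from 5% to 32%. The section 2.3.4 exclusions alone could raise it to between 6% and 20% at ρ = 0.5. As written, a difference between fasting and fed infants could be reported as a randomised effect of vitamin D, so this needs correcting before results are reported.

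**What to change.** 1. **Relabel.** In sections 2, 2.1, 2.2 and 2.4, describe a randomised comparison of two doses with a concurrent non-randomised antibiotics-only cohort.
2. **Keep the contrast, limit the claim.** Report vitamin D versus antibiotics alone for both scores and CRP as a non-randomised estimate adjusted for the Day-0 value and gestational age. Any further covariate from the section 4.2 table, such as birth weight or respiratory support, should be fixed before outcomes are examined. State the endpoint form. State that adjustment cannot separate feeding from vitamin D, so no causal claim is made. Add Day-0 scores and CRP by group to the section 4.2 table.
3. **Reconcile sections 2.3.2, 2.3.4 and 3.4.** Suggested text for 3.4:

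> All randomised infants are analysed in their allocated dose group for 800 v 400 IU. All enrolled infants, including those whose feeding status changes, are followed to Day 7 and analysed in their entry group for the non-randomised contrast. The number whose feeding status changes is reported by group.

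   Amend 2.3.4 to match. The documents do not say whether a Group 1 infant who starts feeding comes under the supplementation step in section 2.7; that must be reconciled too. If Day-7 data were not collected for infants already excluded, report their number by group and state the limitation.
4. **Name the randomised comparison.** Identify 800 v 400 IU as the only one, and state that 19 per arm gives 80% power (two-sided 5%) only for about 0.93 SD. Making it primary is the sponsor's decision. Sections 2.4, 2.5.1 and 3.7 are partly in the past tense, so trial status is unclear; if outcome data have been seen, the primary objective should not be switched.

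**Cost.** Text changes to sections 2, 2.1, 2.2, 2.3.4, 2.4, 3.4 and the 4.2 table, plus 2.3.2 if its wording must change. Assessments at the start and end of treatment and Day-0 and Day-7 blood samples are already planned, and Day 0 is already the baseline (section 3.3), so relabelling and adjustment need no new procedures. Infants whose feeding status changes need a Day-7 assessment, and the claim against antibiotics alone becomes supportive only.
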